PROTOCOL TITLE

Neuromodulation of placebo and nocebo effects

IDENTIFIER

NCT03102710

DATE

4/30/2019

BIOSTATISTICAL ANALYSIS

Specific Aim 1: Characterize the neural mechanisms by which tDCS to rDLPFC modulates placebo / nocebo responses in healthy subjects in an acute pain paradigm.

Primary outcome: 1) fMRI signal changes evoked by identical experimental pain in different conditions (before and after different inert creams) after different tDCS interventions; 2) placebo and nocebo effect difference (as indicated by pain rating differences) after different tDCS interventions.

Similar to our previous studies [1-3], fMRI data processing and statistical analyses will be carried out using SPM8 (<http://www.fil.ion.ucl.ac.uk/spm/>). Preprocessing will include co-registration, motion correction, normalization to MNI stereotactic space, and spatial smoothing with an 8 mm Gaussian kernel. Then, for each subject, the nine contrasts (placebo, nocebo and control condition by pain anticipation, pain administration and pain rating) with the fixation (baseline) will each be calculated using a general linear model.

Group analysis will be performed using a random-effects model. A full factorial module in SPM 8 will be performed to test the differences between the inert Lidocaine, Capsaicin and control creams during pain anticipation, application and intensity ratings separately within each group; then we will compare the differences (between the Lidocaine and control, and Capsaicin and control) among the three groups (tDCS inhibition, tDCS enhancement and sham tDCS) to investigate how tDCS can modulate the placebo and nocebo effects. Covariates including LOT, ERS, STAI scores, gender, and experimenter effect will also be included in the model.

In addition, a multiple regression analysis will be performed between the placebo and nocebo effects as indicated by subjective pain rating differences and corresponding fMRI signal differences by pooling the data of all three groups (group indicator will be included in the model as a covariate). Covariates will include LOT, ERS, STAI scores, gender, and experimenter effect. As in previous studies [2, 4-6], a threshold of voxel-wise $p < 0.005$ with 20 contiguous voxels will be used for pre-defined ROIs. For non-ROI, a threshold of voxel-wise $p < 0.005$ and cluster level $p < 0.05$ Family-wise Error (FWE) corrected will be used.

Specific Aim 2: Characterize the neural mechanisms by which tDCS to rDLPFC modulates functional connectivity of the rDLPFC

Primary outcome: rDLPFC functional connectivity changes before and after different tDCS intervention

Seed based functional connectivity analysis Seed based FC will be applied with a method used in our previous studies [3, 7-10]. In summary, the fMRI data will be preprocessed using Data Processing Assistant for Resting-State fMRI (DPARSF) software [11, 12]. The preprocessing will include slice timing correction, head-motion correction, spatial registration to respective structural images for each subject, 6 rigid body motion, white matter and cerebrospinal fluid signals will be regressed out. After linear de-trending, data will be filtered using a temporal bandpass (0.01-0.08 Hz), and finally smoothed using a full width half maximum of 6 mm. FC analysis for individual subjects will be carried out in DPARSF by applying the seed-based approach. In this study, we will use rDLPFC [13, 14] as seed.

Group analysis will be performed using the random effect model with SPM8. A full factorial model module in SPM8 will be applied: three groups (excitability enhancement, inhibition and sham), two tDCS (first and third) with two conditions (pre and post-treatment). To investigate the incremental effect across the first and last tDCS, we will compare pre- and post-treatment differences in tDCS 1 and 3 of each group. To investigate the incremental effect across three time points, we will also apply the same analysis on the pre-tDCS rsFC in tDCS 1 and 3. In addition, a multiple regression analysis will be performed between the placebo and nocebo effects (indicated by subjective pain rating differences between Lidocaine / Capsaicin and the control condition) and rsFC after the third tDCS by pooling the data of all three groups (group indicator will be included in the model as a covariate). LOT, ERS, STAI scores, gender, and experimenter effect will also be included as covariates in the analysis. A threshold of $p < 0.005$ will be applied for the region of interest. A threshold of $p < 0.001$ uncorrected and $p < 0.05$ corrected will be used for non-ROI brain areas.

Reference

-
1. Kong, J., R.L. Gollub, G. Polich, I. Kirsch, P. Laviolette, M. Vangel, B. Rosen, and T.J. Kaptchuk, *A functional magnetic resonance imaging study on the neural mechanisms of hyperalgesic placebo effect*. J Neurosci, 2008. **28**(49): p. 13354-62 PMCID: PMC2649754.

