PROTOCOL TITLE

Neuromodulation of placebo and nocebo effects

IDENTIFIER

NCT03102710

DATE

4/30/2019

SPECIFIC AIMS

Specific Aim 1: Characterize the effect of applying tDCS to the rDLPFC to modulate placebo and nocebo effects in healthy subjects

Hypothesis 1.1: In the sham tDCS group, placebo lidocaine and capsaicin will produce a significant pain rating decrease (placebo) and increase (nocebo) respectively, in response to identical heat pain stimuli as compared to a within-subject control “neutral” cream. Both effects will be augmented by tDCS enhancement of rDLPFC excitability and blunted by tDCS inhibition of rDLPFC excitability.

Hypothesis 1.2 In the sham tDCS group, placebo treatment will produce fMRI signal increases in regions associated with the DPMS including the DLPFC, orbital prefrontal cortex (OPFC), rostral anterior cingulate cortex (rACC), periaqueductal gray (PAG), and fMRI signal decreases in pain intensity sensitive regions (insula and secondary somatosensory cortex, S2), as compared to the within-subject control in response to identical pain stimuli. These changes will increase in the tDCS enhancement cohort and blunt in the inhibition cohort.

Hypothesis 1.3 In the sham tDCS group, nocebo treatment will produce fMRI signal increases in brain regions associated with cognition and anxiety, including DLPFC, hippocampus, and OPFC, along with fMRI signal decreases in the areas associated with the affective component of pain (dorsal anterior cingulated cortex (dACC) and insula), as compared to the within-subject control neutral cream. These fMRI signal changes will be blunted in the tDCS inhibition group and increased in the tDCS enhancement group.

Specific Aim 2: Characterize how tDCS to rDLPFC can modulate functional connectivity of rDLPFC

Hypothesis 2: Enhancing rDLPFC excitability will increase resting state functional connectivity (rsFC) between the rDLPFC and rACC and insula whereas inhibiting rDLPFC excitability will decrease rsFC between the rDLPFC and rACC and insula as compared with sham tDCS. The rsFC between rDLPFC and rACC will be associated with placebo effect as indicated by pain rating difference.

STUDY PROCEDURES

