We will recruit healthy subjects for this study. Please see the [Protection of Human Subjects](#) section for detailed entry criteria for screening and recruitment. In this experiment, subjects will be randomly assigned to three groups (26 per group): 1) tDCS enhancement group to increase the excitability of rDLPFC, 2) tDCS inhibition group to decrease the excitability of rDLPFC, and 3) sham tDCS group.

Subjects will participate in five experimental sessions: a training and familiarity session, contextual learning/expectancy boost session, two tDCS sessions, and a session combining tDCS and testing for placebo/nocebo effects. Sessions 1 and 2 will be separated by 2-5 days, sessions 2 and 3 will be separated by 1-5 days, then sessions 3, 4, and 5 will be applied on consecutive three days. We will measure tDCS effects via changes in subjective pain ratings, fMRI signals in response to calibrated heat pain and the rsFC.

Detailed experimental procedure

Noxious heat stimuli will be delivered using a PATHWAY system (Medoc Advanced Medical Systems). All stimuli will be initiated from a baseline temperature of 32 °C and increased to a target temperature. Each stimulus will be presented for 12 seconds, including 2.5 seconds to ramp up to the target temperature and 2.5 seconds to ramp down to baseline again. Heat stimuli will be applied to the right volar forearm. **In sessions where tDCS is applied we will administer the tDCS sensation questionnaire to ensure subjects did not have any unexpected adverse reactions.**

Randomization Subjects will be randomized into one of three groups using a centrally generated variable-sized block design: tDCS enhancement, tDCS inhibition, and sham tDCS groups.

Session 1 is a training, familiarity, and calibration session. Subjects will be trained to use the Sensory Gracely Scale (0-20) [1, 2] to rate pain experiences using the same method as in our previous studies [3, 4]. Subjects will first receive an ascending heat stimulus sequence (starting from 38 degrees). The three temperatures that each subject rates as approximately 5-6 (mild pain), 10-11 (moderate pain) and 14-15 (strong pain) will be selected. Subjects will receive a urine drug test on this day to determine no substance abuse.

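### The SPM8 full factorial models take several images per person without saying how those images are linked; run as if independent, they would lose power for the within-person contrasts

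*SAP*

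**What the plan says.** Protocol, Hypothesis 1.2, defines the cream effect "as compared to the within-subject control in response to identical pain stimuli". It then asks a between-group question about that effect: "These changes will increase in the tDCS enhancement cohort and blunt in the inhibition cohort". Study Procedures plans three groups of 26, and in Session 5 every participant is tested with all three creams.

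SAP, Specific Aim 1, forms nine condition-against-fixation images per person (three creams by three phases). It continues: "Group analysis will be performed using a random-effects model". The next sentence reads "A full factorial module in SPM 8 will be performed to test the differences between the inert Lidocaine, Capsaicin and control creams", separately by phase and within each group, "then we will compare the differences (between the Lidocaine and control, and Capsaicin and control) among the three groups". On covariates: "Covariates including LOT, ERS, STAI scores, gender, and experimenter effect will also be included in the model".

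SAP, Specific Aim 2, specifies one SPM8 full factorial with three groups, two tDCS sessions (first and third) and two time points (pre and post), which is four images per person. It again calls the model a random-effect model. It adds that pre-to-post differences at the two sessions will be compared within each group, and that the pre-tDCS images of the two sessions will be analysed in the same way.

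The terms named in these models are group, condition and person-level covariates. No subject factor, dependence setting or covariance structure appears.

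**The concern.** The questions in both aims are about differences within a person. Such a contrast is precise because whatever is common to a person's images cancels. A model that treats the images as independent leaves that common part in the error term, so the standard error of the contrast is too large.

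fMRI signal change by cream and tDCS group is a primary outcome of Aim 1, and change in rDLPFC connectivity is the primary outcome of Aim 2. At stake is the chance of missing real effects with 26 people per arm, by an amount set by an unstated analyst's choice. Two analysts following this SAP could produce different maps from the same data.

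A second question is what the listed covariates do. A reader would expect them to adjust the cream contrasts. In a stacked model with one slope per covariate, they do not.

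**Working it through.** **Inputs.** From the documents: 26 per group, three groups (78 people); three images per person per phase (Aim 1) and four (Aim 2); voxel-wise p < 0.005 in regions of interest, sidedness not stated. Assumed: within-person correlation ρ from 0 to 0.7, equal variances and correlations across conditions, and an effect sized to give 80% power on difference images. The documents give no power calculation, SD or correlation, so there is no stated figure to reproduce.

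**Step 1, standard error.** In a group of n, the true variance of a cream-minus-control mean is 2σ²(1−ρ)/n. An independence model uses 2σ²/n. The t statistic therefore shrinks by √(1−ρ). The same factor applies to the between-group difference of that contrast and to the pre/post contrasts.

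**Step 2, normal approximation, one-sided 0.005.** Power = P(Z > 2.576/√(1−ρ) − (2.576 + 0.842)).

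| ρ | 2.576/√(1−ρ) | actual error rate | power |
|---|---|---|---|
| 0 | 2.576 | 0.0050 | 80% |
| 0.1 | 2.715 | 0.0033 | 76% |
| 0.2 | 2.880 | 0.0020 | 71% |
| 0.3 | 3.079 | 0.0010 | 63% |
| 0.5 | 3.643 | 0.00013 | 41% |
| 0.7 | 4.703 | 0.000001 | 10% |

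Two-sided 0.005 gives 70/62/37/7% at ρ = 0.2/0.3/0.5/0.7.

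**Step 3, simulation with actual degrees of freedom, no covariates.** Power if images are treated as independent, against about 80% for difference images in every row (20,000 runs per setting between groups, 40,000 within group; repeat runs differ by a point or so):

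| ρ | Aim 1, between groups | Aim 2 layout, between groups | Aim 1, within one group |
|---|---|---|---|
| 0 | 81% | 81-82% | 84% |
| 0.1 | 77% | 78% | 81% |
| 0.2 | 71% | 72% | 76% |
| 0.3 | 65% | 65% | 69% |
| 0.5 | 43% | 43% | 48% |
| 0.7 | 12% | 12% | 16% |

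At ρ = 0 the independence model is slightly better because it has more error df (225 against 75 for Aim 1 between groups; 75 against 25 within a group).

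**Step 4, covariates reduce the loss.** If person-level covariates explain a share q of the between-person variance, the independence model's error variance becomes σ²(1−qρ), and 2.576/√(1−ρ) becomes 2.576·√((1−qρ)/(1−ρ)). At ρ = 0.3/0.5/0.7, power is 66/47/15% for q = 0.15 and 69/52/22% for q = 0.30, against 63/41/10% with no covariates. Both q values are assumptions.

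**Step 5, what the covariates adjust.** In the stacked model, person i in group g has image vector μ_g + **1**·(x_iβ) + error, where x_i is constant over that person's images. With complete data the fitted cream means are μ̂_g = ȳ_g − **1**·(x̄_gβ̂). For a cream contrast c with c·**1** = 0, c·μ̂_g = c·ȳ_g. The covariates drop out whatever β̂ is, and whether or not dependence is declared. They can change only the standard error.

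**The case against.** The strongest reply is that this is a reporting gap and not a demonstrated error. A reader might infer that the SAP commits to treating images as independent; it does not. Both group analyses are labelled random-effects, and the named module can be kept if its repeated factors are declared dependent. The SAP also ties its methods to the group's previous studies, which may describe the setting. All of that stands. But the label says that inference is across people; it does not say how three or four images from one person are joined in the factorial, and person-level covariates do not pair them.

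Second, some wording points to differences. In Aim 1, "then we will compare the differences (between the Lidocaine and control, and Capsaicin and control) among the three groups" may mean one difference image per person, and the Aim 2 sentence on pre-to-post differences can be read in the same way. If so, those steps are unaffected. What remains most clearly exposed is the Aim 1 within-group cream comparison, which is described as a factorial over the creams. The four-cell Aim 2 factorial is exposed if it is fitted as written.

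Third, the size of the loss rests on an assumed correlation. It is modest at 0.2 or below and smaller again with useful covariates. This is correct, and the range is shown for that reason.

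Two further inferences are not supported. One is that the plan inflates false positives: with equal variances and positive correlation, the contrasts it names err on the conservative side. The other is that the covariate point shows bias: an unadjusted difference between randomised groups is not biased.

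**Conclusion.** The point holds as a conditional one. The SAP specifies factorial models on repeated images and omits the term or setting that makes them repeated-measures models. If the images are treated as independent, between-group power falls from 80% to about 77/71/65/43/12% at correlations of 0.1/0.2/0.3/0.5/0.7, assuming equal variances, one-sided 0.005 and no covariates. At zero correlation nothing is lost; a negative correlation would reverse the direction. The documents settle neither the correlation nor the handling of dependence, so this is not a finding that the analysis will be wrong.

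The covariate result needs no assumed correlation, only a stacked model, common slopes and complete data. It means that declaring dependence does not by itself make the listed covariates adjust the cream contrasts.

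The point concerns the imaging group models. It does not extend to the regressions on per-person rating differences, and it makes no claim about the pain-rating comparison, for which the SAP states no model. The change should be made because primary outcomes are involved and it is cheap; confidence is medium.

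**What to change.** Write into the SAP that one difference image per person enters each group model:

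- Aim 1, for each phase: lidocaine minus control, and capsaicin minus control.
- Aim 2: post minus pre at tDCS 1 and at tDCS 3; the change between those two differences; and pre-tDCS 3 minus pre-tDCS 1.

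Compare the three groups on each image with the listed covariates. Test within-group effects with one-sample or paired models; centred covariates will not change those means. If the factorial is kept, declare the cream, session and pre/post factors dependent, and add covariate-by-cream terms if the covariates are meant to adjust the cream contrasts. If dependence was always going to be modelled, a sentence saying so settles the power question.

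**Cost.** SAP wording and some batch set-up, with the same software and first-level images. Between-group residual df become 78 − 3 − 5 = 70 if the covariates use five df, or 67 if they use eight (both assumed); within-group df become 25. The expected variance factor for adjusting difference images with p covariate df is (1−R²)(1 + p/(74−p)). At R² = 0 the standard error rises by √(1 + 5/69) = 1.04 or √(1 + 8/66) = 1.06, that is, about 3-6% when the covariates are uninformative. Break-even R² is 5/74 = 0.07 or 8/74 = 0.11. If the true correlation is near zero, difference images give up about 1 point of power between groups and 4 within a group.

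### Must the SAP state whether its fMRI thresholds are one-sided or two-sided, given hypotheses that predict both increases and decreases?

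*SAP*

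**What the plan says.** The SAP gives four thresholds.

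- Aim 1, ROIs: "a threshold of voxel-wise $p < 0.005$ with 20 contiguous voxels will be used for pre-defined ROIs".
- Aim 1, elsewhere in the brain: "a threshold of voxel-wise $p < 0.005$ and cluster level $p < 0.05$ Family-wise Error (FWE) corrected will be used".
- Aim 2, ROI: "A threshold of $p < 0.005$ will be applied for the region of interest".
- Aim 2, elsewhere: "A threshold of $p < 0.001$ uncorrected and $p < 0.05$ corrected will be used for non-ROI brain areas".

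The Aim 1 thresholds stand at the end of the paragraph on regressing fMRI differences on rating differences. The preceding paragraph plans a full factorial model in SPM8 to "test the differences between the inert Lidocaine, Capsaicin and control creams during pain anticipation, application and intensity ratings separately within each group", and then to compare those differences among the three tDCS groups. No sentence gives a sidedness or says whether t or F contrasts are used.

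The protocol's Specific Aims give the directions. Hypothesis 1.2 (placebo) predicts increases in DLPFC, OPFC, rACC and PAG, and "fMRI signal decreases in pain intensity sensitive regions (insula and secondary somatosensory cortex, S2". Hypothesis 1.3 (nocebo) predicts increases in hippocampus, OPFC and DLPFC, "along with fMRI signal decreases in the areas associated with the affective component of pain (dorsal anterior cingulated cortex (dACC) and insula". Hypothesis 2 predicts that enhancement raises rDLPFC connectivity with rACC and insula, "whereas inhibiting rDLPFC excitability will decrease rsFC between the rDLPFC and rACC and insula as compared with sham tDCS".

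**The concern.** Pain-evoked fMRI signal is the first-listed primary outcome of Aim 1, and rDLPFC connectivity is the primary outcome of Aim 2. The hypotheses contain both increases and decreases, so an analyst will look at positive and negative contrasts. If each is tested at the stated p, the two together have twice the stated error rate: 0.01 instead of 0.005 per voxel, and up to 0.10 instead of 0.05 for a corrected whole-brain search. An effect falling between the two critical values would be a finding under one reading and not under the other, and the text does not settle which applies.

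The insula raises a second doubt. Hypothesis 1.2 groups it with regions that track pain intensity and expects its signal to fall under placebo. Hypothesis 1.3 expects it to fall under nocebo too, although Hypothesis 1.1 expects more pain there. That can look like a sign error, which would affect how Hypothesis 1.3 is judged.

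**Working it through.** The plan reports no power or error-rate calculation, so there is no figure of its own to reproduce. The inputs from the documents are the four thresholds, the 8 mm smoothing kernel for Aim 1 and 26 subjects per group. Everything else below is marked as an assumption.

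**1. Critical values.** Assume one paired contrast in the sham group, df = 26 − 1 = 25. This is simpler than the planned factorial model with covariates.

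- 0.005 in one direction: t(0.995; 25) = 2.787.
- 0.005 over both directions: t(0.9975; 25) = 3.078.
- Large-sample equivalents: z = 2.576 and 2.807. For the Aim 2 non-ROI level of 0.001: z = 3.090 and 3.291.

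**2. Error rate per voxel under each reading.**

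- One-sided, predicted direction only: 0.005.
- Two-sided: 0.0025 + 0.0025 = 0.005.
- Both directions, each at 0.005: 0.005 + 0.005 = 0.010.

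Only the third reading exceeds the stated level.

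**3. Do the hypotheses require the third reading in the ROIs?** Hypothesis 1.2 makes 4 + 2 = 6 regional predictions and Hypothesis 1.3 makes 3 + 2 = 5. Each of the 11 has one sign for one region and one cream. The two signs in Hypothesis 2 belong to different contrasts (enhancement against sham, inhibition against sham), not to two tails of one contrast. Positive and negative predictions therefore coexist without any single prediction needing both tails.

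**4. Effect on the 20-voxel ROI rule.** Assume null Gaussian fields in a 30 mm cube and 18-neighbour clusters of at least 20 voxels. Voxel size and final smoothness are also assumed. The chance of at least one such cluster, by simulation, is:

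| Voxel, smoothness | Predicted tail only, z > 2.576 | Two-sided, z > 2.807 each way | Both tails, z > 2.576 each way |
|---|---|---|---|
| 3 mm, 8 mm | 0.020 | 0.011 | 0.040 |
| 3 mm, 10 mm | 0.047 | 0.037 | 0.099 |
| 2 mm, 8 mm | 0.23 | 0.21 | 0.41 |
| 2 mm, 10 mm | 0.25 | 0.25 | 0.43 |

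The two conventional readings (first two columns) differ by a factor of 0.020/0.011 = 1.8 at most and 0.25/0.25 = 1.0 at least. The larger rates in the last column arise only from the third reading.

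**5. Outside the ROIs.** No direction is predicted here. With the corrected 0.05 applied to each direction, the rate per contrast is 1 − 0.95² = 0.0975 if the directions are independent, and at most 0.05 + 0.05 = 0.10. With 0.025 in each direction it is at most 0.05.

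**6. Cost of a blanket two-sided rule.** Power at one voxel is 1 − F(c; 25, d√26), where F is the noncentral t distribution function and c the critical value. Moving c from 2.787 to 3.078 loses 0.044, 0.074, 0.099, 0.105 and 0.062 at assumed d = 0.3, 0.4, 0.5, 0.6 and 0.8. For a prediction tested only in its stated direction, this loss buys no lower voxel-wise rate: it is 0.005 either way.

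**7. F contrasts.** Comparisons across three creams or three groups may be run as omnibus F tests. These have no direction, so a rule of half the p value per direction has no meaning for them, and the doubling does not arise.

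**8. Insula.** Hypothesis 1.3 gives a sign (decrease) and a reason (the affective component of pain), and it gives dACC the same sign in the same clause. Falling under both creams is unusual but not contradictory. As for phase, the SAP's Aim 1 primary outcome is the signal evoked by identical experimental pain, which points to pain administration.

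**The case for a change.** The strongest case for acting is that the gap concerns primary outcomes, one sentence would close it, and the choice is better made before results are seen. Prespecified directions also do not cover everything. The non-ROI search has no predicted sign. Nor do the regressions on rating differences: Hypothesis 2 predicts an association between rDLPFC–rACC connectivity and the placebo effect without saying which way, and the Aim 1 thresholds sit in the regression paragraph. If those thresholds cover the regressions alone, the factorial analysis has none of its own.

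Much of this stands as a description. Sidedness and contrast type are unwritten, and applying the Aim 1 thresholds to the factorial contrasts is an inference. Where no sign is predicted, a two-sided test is the ordinary default, and it keeps the stated rates. What does not stand is the step from an unwritten convention to an inflated error rate. That needs both tails to be searched at the full level, and the SAP does not say so. Nor does a single two-sided rule for every contrast follow: it is debatable for directional ROI hypotheses and undefined for F tests.

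Sidedness is also the smaller influence on the ROI rule. With 2 mm voxels, the two-sided reading itself gives 0.21 to 0.25 per assumed region, so the uncorrected threshold matters more than the number of tails.

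**Conclusion.** No change follows. The SAP leaves a convention unstated, and analysts can fill it sensibly: the predicted direction, or a two-sided test, for ROI contrasts whose sign the protocol fixes; a two-sided test, with the corrected 0.05 split as 0.025 per direction, where no sign is predicted and signed contrasts are searched both ways. Either choice keeps the voxel-wise ROI rate at 0.005 and the non-ROI rate at no more than 0.05 per contrast. A report that gives contrast type and direction beside each result lets readers see which was used.

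The residual ambiguity is bounded. For a paired contrast with 25 df, it affects effects with |t| between 2.79 and 3.08. Outside the ROIs, where the protocol states no hypotheses, the worst case is 0.10 instead of 0.05 per contrast. The cluster rates rest on an assumed region size, voxel size and smoothness and serve only to compare the readings. The insula query changes no analysis, because Hypothesis 1.3 already states the sign against which it will be judged.

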At the end of the experiment, subjects will be debriefed by a licensed physician or by the Principal Investigator, [name]. We will inform them that in this study, only inert cream and sham tDCS (in session 2 or in sham tDCS group) was used, and that we changed the heat pain temperature at session 2. We will also emphasize that the experience of this study should not influence their impression of lidocaine / capsaicin or their interest in choosing these drugs as a potential therapeutic method.

Transcranial direct current stimulation (tDCS) administration

Twenty minutes of tDCS at 2mA will be applied by the StarStim system. For the rDLPFC excitability inhibition group, the cathodal electrode will be placed over F4 and the anodal electrode above the left orbit. For the rDLPFC excitability enhancement group, the anodal electrode will be placed over F4 and the cathodal electrode above the left orbit. Stimulation will start and finish with a 15 second gradual current ramp up and ramp down to decrease subjects' discomfort. For sham tDCS treatment, stimulation will be applied only at ramp periods at the beginning and end of sham stimulation to mimic the somatosensory effect of real tDCS for 15 s. As in a previous study [7], the electrodes will be placed at the same positions for the real tDCS (half rDLPFC enhancement position, half rDLPFC inhibition position).

fMRI data acquisition

The MRI scan will be performed using a 3 Tesla Siemens MRI System equipped for Echo Planar Imaging using a 32 channel head coil. fMRI data will be acquired using gradient echo T2*-weighted sequence (TR/TE=2000/30 msec, flip angle=90°, slice thickness=3 mm). The scans will include pre-tDCS resting state (8 minutes) and post-tDCS resting state (8 minutes) scans during the application of heat pain stimuli to different spots. For pain stimuli at each spot, a paradigm used in our previous study [8] will be applied, which include

anticipation, pain and pain rating, each pain sequence at one spot lasts about 5 minutes (**Figure 6**). A high-resolution 3D MPRAGE sequence with 1 mm³ isotropic resolution will also be collected for anatomic localization of the fMRI signal changes. tDCS (20 minutes) will be applied in the scanner as our tDCS device is MRI compatible.

Reference

1. Gracely, R.H., P.A. McGrath, and R. Dubner, *Ratio scales of sensory and affective verbal pain descriptors*. Pain, 1978. **5**: p. 5-18.

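### Aim 1's cluster-level 5% error outside the ROIs is not assured at a voxel threshold of p<0.005

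*SAP*

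**What the plan says.** The SAP, Specific Aim 1, gives two imaging thresholds. Inside the hypothesised regions, "a threshold of voxel-wise $p < 0.005$ with 20 contiguous voxels will be used for pre-defined ROIs". Elsewhere, "For non-ROI, a threshold of voxel-wise $p < 0.005$ and cluster level $p < 0.05$ Family-wise Error (FWE) corrected will be used". The appeal to previous studies is attached to the ROI rule, not to the second rule. Both follow a paragraph on a pooled regression. I read them as covering all Aim 1 group maps, since no other Aim 1 threshold is given.

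On method, the SAP says "fMRI data processing and statistical analyses will be carried out using SPM8", after "spatial smoothing with an 8 mm Gaussian kernel". It mentions no permutation test.

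For Aim 2 (resting-state connectivity, also analysed at group level in SPM8, but "smoothed using a full width half maximum of 6 mm"), the SAP says: "A threshold of $p < 0.001$ uncorrected and $p < 0.05$ corrected will be used for non-ROI brain areas". This names neither the level of the correction (voxel or cluster) nor its type (FWE or other). No reason is given for the different voxel thresholds.

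**The concern.** A parametric cluster test asks how large a cluster chance alone would produce. It answers from one estimated smoothness value and an approximation that works best at a high voxel threshold. If part of the noise is correlated over longer distances than a Gaussian shape allows, as motion or physiological noise could be, chance clusters grow larger than the formula expects. A looser voxel threshold lets more of them form. Aim 1's voxel threshold is five times looser than Aim 2's (0.005 / 0.001 = 5).

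Pain-evoked fMRI change is listed first under Aim 1's primary outcome. The between-arm comparison alone covers two cream contrasts in three task phases (2 x 3 = 6 maps), so any excess error would recur. Outside the ROIs no regional hypothesis is stated against which to check a chance cluster, so the FWE label is the main protection there.

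**Working it through.** **What can be reproduced.** The 5% is a chosen nominal level, not a derived figure, so the check is whether the rule would deliver it.

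**Inputs from the documents.** Voxel p<0.005, cluster FWE 0.05, 8 mm smoothing and SPM8 (SAP, Aim 1); voxel p<0.001 (SAP, Aim 2). From the Protocol, Study Procedures: "subjects will be randomly assigned to three groups (26 per group", so 3 x 26 = 78 subjects and 78 - 3 = 75 residual df before covariates. From the Protocol, fMRI data acquisition: "slice thickness=3 mm", the basis for an assumed 3 mm analysis voxel.

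**Assumptions not in the documents.** Brain volume about 1.4 L, 18-neighbour clusters, the noise shapes below, and the random-field formula taken to be SPM8's default:

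- P(size >= k) = exp(-b k^(2/3)), with b = (Gamma(5/2) / E[n])^(2/3)
- FWE p = 1 - exp(-E[m] x P)

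E[m] is the expected number of clusters and E[n] their mean size in voxels.

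**Step 1: the cut-off, by hand (volume term only, estimated smoothness 8.4 mm).**

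Voxels = 1,400,000 / 27 = 51,852. Resels = 1,400,000 / 8.4^3 = 2,362. Clusters per resel = (4 ln 2)^(3/2) / (2 pi)^2 x (u^2 - 1) x exp(-u^2 / 2).

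| | p<0.005 | p<0.001 |
|---|---|---|
| u | 2.576 | 3.090 |
| Clusters per resel | 0.02388 | 0.00844 |
| E[m] = 2,362 x that | 56.4 | 19.9 |
| E[n] = p x 51,852 / E[m] | 4.60 | 2.60 |
| b | 0.437 | 0.639 |
| P needed = -ln(0.95) / E[m] | 0.00091 | 0.00257 |
| k = (-ln P / b)^(3/2) | 64.1 | 28.5 |

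The full calculation used 66 and 29 voxels; a small gap is expected because the hand version keeps only the volume term. Smoothness is the only feature of the noise that enters.

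**Step 2: simulation A.** 26 null images, 25 df, 1,437 cm3 sphere, 8 mm smoothing, one direction. An assumed share of the noise variance has a 24 mm range.

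| Long-range share | Error at 0.005 (exact 95% CI) | Error at 0.001 |
|---|---|---|
| 0% | 4/389 = 1.0% (0.3-2.6%) | 6/389 = 1.5% |
| 10% | 11/257 = 4.3% (2.2-7.5%) | 7/257 = 2.7% |
| 20% | 20/248 = 8.1% (5.0-12.2%) | 8/248 = 3.2% |
| 30% | 57/495 = 11.5% (8.8-14.7%) | 25/495 = 5.1% (3.3-7.4%) |

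**Step 3: simulation B.** Ellipsoid brain, different noise shapes, 900 null maps (1,800 one-directional tests) per scenario.

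| Noise | Error at 0.005 | Error at 0.001 |
|---|---|---|
| Gaussian-shaped, about 8, 10, 12 mm | 0.6%, 1.2%, 1.3% | 1.1%, 1.5%, 1.7% |
| Short exponential tails (5-8 mm) | 4.5% to 5.2% | 3.7% to 4.3% |
| Long tails (15 mm) | 13.1%, 16.2% | 7.1%, 7.7% |

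The Monte Carlo standard error is about 0.2 points at 1% and 0.9 points at 16%.

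The mechanism shows in two of these scenarios. A short-tailed field and a long-tailed field had almost the same estimated smoothness (11.5 and 11.4 mm), hence almost the same cut-off at 0.005 (139 and 136 voxels). Their errors were 5.1% and 16.2%.

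**Step 4: sensitivity checks.**

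- Full 3 x 26 design, t map on 75 df, 120 one-directional tests each: 1.7% (Gaussian, 8 mm) and 20.0% (long tails) at 0.005; 1.7% and 8.3% at 0.001.
- A variant of the formula, with mean cluster size from the total Euler characteristic, gave 2.2% to 4.7% (Gaussian), 11.5% to 12.5% (short tails) and 21.9% to 23.9% (long tails) at 0.005.
- Counting a false cluster in either direction roughly doubles each figure (1.2% to 30.3% with the main formula at 0.005).

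**The case against.** The percentages come from assumptions. The documents give no noise autocorrelation, achieved smoothness, analysis voxel size or sidedness, and they name SPM8 but no formula. With short-tailed noise, changing only the formula moves the error from about 5% to about 12%. With Gaussian-shaped noise the rule is conservative, and in simulation A the excess is clear only at the 30% share; at 20% the interval starts at 5.0%. All of this stands. A reader might infer that the rule exceeds 5%, or that 12% or 16% is a ceiling; the documents support neither.

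A reader might also infer that the two aims contradict each other. They do not: Aim 2 is a different analysis with different smoothing, and its wording does not say that its 0.05 is cluster-level FWE. The difference is unexplained, not inconsistent.

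Simulation A is a one-group test, not the between-arm contrast. The full-design check answers this in part, but with only 120 tests per scenario.

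Finally, the rule leaves the pain ratings and the regions named in Hypotheses 1.2 and 1.3 untouched. That limits the importance of the point. It does not supply a reason for the looser threshold or a check on the error rate.

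**Conclusion.** The point holds as a lack of assurance. If the standard parametric test is used, the actual per-direction error of the Aim 1 non-ROI rule could lie well below or well above 5%, depending on noise that the documents do not describe: about 1% to 16% with the main formula over the scenarios tried. That range is illustrative and not a bound. Two simulations with different brain shapes and noise models agree on the direction and on the lower end.

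The threshold of 0.001 is less sensitive to noise shape but is not a cure: it still reached 7% to 8% under long tails. The reach is limited to areas outside the pre-defined ROIs. I would class this as a cheap improvement.

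**What to change.** For Aim 1 non-ROI areas, take the cluster-level FWE p-value from a permutation test:

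- For between-arm contrasts and the pooled regression, use a scheme that handles the planned covariates (LOT, ERS, STAI, gender, experimenter), for example permuting residuals from the reduced model. Plain shuffling of arm labels ignores the covariates and does not cover the regression. With covariates, control of the error is approximate.
- For within-arm contrasts, flip the signs of the difference images and state the assumption of symmetric errors.

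At minimum, set the cluster-forming threshold to p<0.001 and acknowledge that this reduces the dependence on noise without removing it.

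In both aims, state that the 0.05 correction is cluster-level FWE, and say whether tests are one- or two-directional.

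The cost is a few SAP sentences and computing time. With the stricter threshold there is also less sensitivity to weak, widespread clusters outside the hypothesised regions.
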